Post Authorization Utilization Study Protocol

Title	Claims database study of utilization patterns of dimethyl fumarate in Germany
Protocol ID:	109MS409
Protocol version	FINAL 1.0
Date of last version of protocol	06 OCT 2014
EU PAS register number	Study to be registered prior to start of data analysis
Active substance	Dimethyl fumarate (DMF) ATC classification: N07XX09
Medicinal product	Dimethyl fumarate (Tecfidera®), 120 mg and 240 mg gastro-resistant hard capsule,
Product reference	EU/1/13/837/001 (120 mg) EU/1/13/837/002 (240 mg)
Procedure reference	EMA/H/C/2601
Marketing authorization holder:	Biogen Idec MA Inc. Biogen Idec Research Limited
Joint PASS	No
Research question and objectives	
Primary objective:
 
 - To estimate the proportion of DMF use that is prescribed “on-label” versus “off-label”. 
Secondary Objectives
 
 - To describe the demographic characteristics and medical history of DMF users. - To describe prescription drug history and concomitant medication use of DMF users. - To describe the duration of therapy in patients newly initiating DMF treatment. - To describe the medical specialties of DMF prescribers.
Country of study	Germany
Main Author:	
██████████, PhD, Biogen Idec
 
██████████ ██████████, Biogen Idec MA Inc.
 
Tel.: ██████████

CONFIDENTIAL
 
The information and data included in this protocol contain trade secrets and privileged or confidential information which is the property of the Sponsor. No person is authorized to make it public without written permission of the Sponsor. These restrictions on disclosure will apply equally to all future information supplied to you which is indicated as privileged or confidential. This material may be disclosed to and used by your staff and associates as it may be necessary to conduct the clinical study.
	

Marketing authorization holder

Marketing authorization holder:	Biogen Idec MA Inc. [name] Biogen Idec Research Limited [name]
MAH contact person	[REDACTED], MD, PhD [REDACTED] [REDACTED] Biogen Idec Research Limited Tel.: [REDACTED]

1 Signature Pages

Research Question and Objectives	
The primary objective of this study is to estimate the proportion of DMF use that is prescribed “on-label” versus “off-label”.
 
The secondary objectives of this study are to:
 
Describe the demographic characteristics, medical history, prescription drug history, and concomitant medication use of DMF users. Describe the duration of therapy in patients newly initiating DMF treatment. Describe the medical specialties of DMF prescribers.

Study Design	
Retrospective analysis of a research database, which contains German sick fund claims, to assess the usage of DMF in Germany. The data are fully pseudonymized and contain information on demographics, diagnosis, and medical prescriptions, as well as inpatient and outpatient treatment.
 
The study data collection period will include the 6 month period prior to the German market introduction of DMF and end at 18-22 months after market introduction (depending on date of data availability). The research database is updated annually; data analyses will be based upon the first database update containing data for the initial 18 months of DMF market availability in Germany. It is assumed that a 6 month pre-DMF launch observation period is sufficient to establish baseline characteristics of patients initiating treatment with DMF and a minimum of 18 months will be sufficient to see initial uptake of DMF in the MS market, any off-label use (per product information), and subsequent potential uptake in other therapeutic areas.

Population	All new users of DMF during the study period will be eligible for the analysis. The patient index date is defined as the date of first filled prescription for DMF. New users will be defined as patients without a previous prescription for DMF in the 6 months prior to the index date. Patients for which the 6 months prior to the index date is not available will be excluded from the analysis.

Variables	The primary analysis will focus on the use of DMF, which will be identified by pharmacy claims containing the anatomical therapeutic chemical (ATC) classification system code N07XX09. "Off-label" use is defined as any DMF prescription for MS patients <18 years of age, or for patients diagnosed with non-MS indications, such as psoriasis. Discontinuation will be assessed by a calculated gap in prescriptions of 4-6 weeks, with the exact length of the medication gap defined according to the most common pack size. The date of the first pharmacy claim for DMF will be used as the index date for this study.	
Data sources	The research database is comprised of German sick fund data, which is compiled by Gesundheitsforen Leipzig (GFL). This GFL database currently contains sick fund claims data for approximately 4 million patients, which accounts for approximately 5-6% of the total sick fund population in Germany. The GFL database contains current data up to 2012 and is updated on an annual basis.	
Study size	Based on a feasibility analysis and preliminary market uptake projections, approximately 500 MS patients in the GFL research database are expected to initiate treatment with DMF within 18 months of product launch in Germany. The actual sample size of the study will depend on the actual market uptake of DMF.	
Data analysis	This study is strictly descriptive (i.e. no hypothesis testing is being conducted). Demographic characteristics, concomitant medication, medication history, time on DMF and specialty of prescribing physician will be analysed separately by "on-label" or "off-label" use. All statistical analyses will be reported in a descriptive manner. Continuous data will be described by their mean, standard deviation, median, minimum, and maximum. Categorical data will be described by absolute and relative frequencies. A detailed description of the statistical analysis will be provided in the statistical analysis plan.	
Milestones	
 • Final study protocol • Start of data retrieval and data analysis • Final study report 	
06 October 2014
 
Q4 2016
 
Q4 2017

6 Amendments und Updates

None

7 Milestones

Milestones	Planned date
Final study protocol	06 October 2014
Registration in the European Union (EU) Post-Authorization Study (PAS) register	After finalization of protocol
Start of data collection (date from which data extraction starts)	01 September 2013
End of data collection	31 December 2015
Start of data retrieval and data analysis	Q4 2016
Final study report	Q4 2017

DMF was launched in Germany in March 2014. The data collection period will include 6 months prior to the market launch of DMF (starting at 01 September 2013) and cover a minimum of 18 months after market launch of DMF (01 September 2013- 31 December 2015).

Data retrieval will start as soon as sick fund data for the data collection period (years 2013-2015) become available (anticipated in Q4 2016) and data analysis will follow.

The final study report will be submitted within 12 months after start of data retrieval. No interim analysis or interim reports will be produced.

8 Rationale and Background

Multiple sclerosis (MS) is primarily an inflammatory disorder of the brain and spinal cord in which focal lymphocytic infiltration leads to damage of myelin and axons(1). Considerable social and economic consequences result from this chronic and progressive disease of the central nervous system. In North America and Europe, MS is the leading cause of non-traumatic neurological disability in young adults, affecting over two million people worldwide.(2) The disease usually presents itself in adults, who are between 20 and 40 years of age, and there is a higher incidence among women.(3)

Tecfidera® is a drug product containing the active ingredient dimethyl fumarate (DMF), which has been developed for the treatment of MS. This active ingredient is rapidly converted into its primary metabolite monomethyl fumarate (MMF). DMF is the first single ester of fumaric acid ester to be investigated in clinical trials.

In subjects with MS, two randomized, controlled Phase 3 clinical studies (109MS301 and 109MS302) concluded that treatment with DMF over 2 years led to significant reductions in the frequency of relapses and the development of brain lesions associated with the disease compared to placebo. Additionally, in study 109MS301, DMF therapy significantly reduced the risk of confirmed (12-week) disability progression (as measured by Expanded Disability Status Scale scores) compared with placebo. DMF also demonstrated a positive benefit-risk balance for the proposed indication of RRMS.

Currently, the standard clinical management of MS patients varies across countries. As a number of new products have recently been introduced, it is unclear how the introduction of DMF will affect treatment patterns in routine clinical practice.

In addition, it is unclear if DMF would be used “off-label” for other inflammatory conditions, including psoriasis. Fumaderm® is a fumarate ester drug product that contains DMF in combination with three different salts of monoethyl fumarate. These salts are pharmacodynamically active and have different active metabolites than DMF. Fumaderm® has been available on the German market for the treatment of psoriasis since 1994.(4;5) Furthermore, Fumaderm® has been used “off-label” for the treatment of psoriasis in children.(6)

This study will provide information on utilization and potential off-label use of DMF, especially with regards to pediatric patients diagnosed with psoriasis. This study is part of a comprehensive risk management plan that also includes pharmacovigilance and drug safety studies.

9 Research Question and Objectives

9.1 Primary Objective

The primary objective of this study is to estimate the proportion of DMF use that is prescribed “on-label” versus “off-label” in Germany.

9.2 Secondary Objectives

The secondary objectives of this study are as follows:

- Describe the demographic characteristics and medical history of DMF users
- Describe the prescription drug history and concomitant medication use of DMF users.
- Describe the duration of therapy in patients newly initiating DMF treatment.
- Describe the medical specialties of DMF prescribers.

10 Research Methods

10.1 Study Design

The study is a non-interventional, retrospective cohort study of a German sick fund claims database to assess the usage of DMF in Germany. The data are fully pseudonymized¹ and contain information on demographics, diagnosis, and medical prescriptions, as well as inpatient and outpatient treatment.

¹ In this protocol the term “pseudonymization” will be to describe the way the data privacy is secured. By pseudonymizing the patient ID is replaced by a unique pseudo-ID in each of the different data tables enabling data sets to be linked from different data sources. It differs from anonymization where the patient ID is replaced by a (different) random number in each occurrence disabling linkage of data.

Patients will be identified based on at least one prescription of DMF. The data collection period will begin 6 months prior to the German market introduction of DMF and end at the earliest 18 months after market introduction. The exact data collection end date will be determined by the availability and completeness of data included in the annual update to the sick fund claims database. It is assumed that a 6 months pre-DMF launch observation period will be sufficient to establish baseline characteristics of patients initiating treatment with DMF and a minimum of 18 months will be sufficient to see initial uptake of DMF in the MS market, any off-label use (per product information), and subsequent potential uptake in other therapeutic areas. The primary outcome of this study is the proportion of DMF used “off-label” in Germany.

In order to observe real-life treatment patterns and “off-label” use, the retrospective research design using sick fund claims data represents a particularly well suited approach. Due to the nature of the data collection, it is assured that there is no influence on patient behavior and no interference by physicians on study procedures and data collection. The high level of detail in the German claims data, including diagnostic codes, allows the efficient and valid identification of “off-label” use, as well as the description of subsequent usage.

10.2 Setting

10.2.1 Study Population

All users of DMF in the post launch study period (time period defined in Section 10.2.3) will be retrieved from the database.

10.2.1.1 Inclusion Criteria

New users of DMF will be included in the analysis. New users are defined as patients without a previous prescription for DMF in the 6 months prior to the index date. The patient index date is defined as the date of first filled DMF prescription. Patients pretreated with products containing different fumarates (i.e. Fumaderm®) may be included in the study.

10.2.1.2 Exclusion Criteria

Patients for which data is not available for the 6 months period prior to the index date (baseline observational period) will be excluded from the analysis.

10.2.2 Research Database

The study will be conducted using data from the sick fund claims contained in a research database collected by GFL during the period 2013-2015. This database currently contains sick fund claims data for approximately 4 million patients, which accounts for approximately 5-6% of the total sick fund population in Germany.

[figure not shown]
The GFL database was chosen as it provides a comprehensive source of inpatient, outpatient, and prescription drug data. Furthermore, the GFL database is fairly representative for the German sick fund market with respect to basic demographic variables. In a recent analysis, the proportion of women was similar in the GFL database compared to the general sick fund market (50.3% vs. 52.9%).⁽⁷⁾ Finally, the data has already successfully been used to explore the treatment and cost of MS in Germany.⁽⁸⁻¹⁰⁾

10.2.3 Study Timeframe

The overall study period will include the data collection period through the final study report and is expected to be approximately 4 years.

The study data collection period will begin 6 months prior to the German market introduction of DMF and will end 18-22 months after market introduction (depending on date of data availability) (Figure 1). The research database is updated annually; data analyses will be based upon the first database update containing data for the initial 18 months of DMF market availability in Germany.

Figure 1. Study time frame

It is assumed that 6 months pre-DMF launch will be sufficient to establish baseline characteristics of patients initiating treatment with DMF. A post-launch observation time of at least 18 months will be sufficient to see initial uptake of DMF in the MS market and subsequent potential uptake in other therapeutic areas.

Analysis will begin once data is retrieved from the GFL database.

10.3 Variables

Preliminary study variables are defined below. Additional variables and further refinements of variable definition will be included in the Statistical Analysis Plan (SAP).

10.3.1 Demographic Variables

Demographic variables to be retrieved from the claims data include:

- Age
- Gender

10.3.2 Diagnosis of Comorbidities

The comorbidities at time of DMF initiation will be recorded by ICD-10 codes with three (3) digits in medication claims, or if available, associated with inpatient or outpatient treatments that are within a time window of 6 months prior to DMF initiation.

10.3.3 "On-label" and "Off-label" Use

DMF "on-label" prescriptions will be primarily defined as prescriptions for patients who are ≥ 18 years of age and diagnosed with MS (see Table 1). The algorithms for identifying "on-label" use will include the presence of at least one medical claim with an ICD-10 code of MS for the indicated conditions (G35.x for MS).

DMF "off-label" prescriptions will be primarily defined as prescriptions for patients without an MS diagnosis or for patients who are < 18 years of age and diagnosed with MS. All non-MS prescriptions will be further characterized by use in patients with and without psoriasis (i.e. patients with no evidence of psoriasis or MS in their claims history during the of 6 months prior to DMF initiation). In addition, all non-MS prescriptions will be further categorized by use in patients < 18 years of age and ≥ 18 years of age.

Table 1. Patient groups considered for "on-label" and "off-label" use

	MS Patients	Non-MS Patients	
	DMF	Psoriasis	Other Diagnosis
Age < 18	Off-label	Off-label	Off-label
Age ≥ 18	On label	Off-label	Off-label

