10.7.3 Primary Analysis

The primary objective of this study is to estimate the proportion of DMF use that is prescribed “on-label” versus “off-label” in Germany. The proportion of “off-label” use will be calculated as:

$$1 - \frac{\text{\# patients using DMF on-label}}{\text{Total \# of DMF patients}}$$

Analyses of “off-label” use will be further described, as shown in Table 2 below. Sensitivity analyses will be performed with regard to patients for whom the diagnostic code is missing.

Table 2. Proportions of “off-label” use (subgroups)

	MS Patients	Non-MS	
		Psoriasis	Other Diagnoses (wt/wo missing diagnoses)
Age <18	n/N [%]	n/N [%]	n/N [%]
Age ≥18	n/N [%]	n/N [%]	n/N [%]

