10.9 Limitations of the Research Methods

10.9.1 General Limitations

The retrospective study design and the nature of claims data are associated with some methodological limitations:

- Presence of a claim for a filled prescription does not indicate that the medication was consumed nor that it was taken as prescribed
- Medications provided in a clinical trial or as samples by the physician will not be observed in the claims data
- Presence of a diagnosis code on a medical claim is not positive presence of disease, as the diagnosis code may have been incorrectly applied
- Important clinical information of interest is not readily available in claims data that could have an effect on study outcomes, such as certain clinical and disease-specific parameters, including e.g. results of magnetic resonance imaging (MRI) scans or further diagnostic information

10.9.2 *Potential Bias*

Due to the voluntary participation of German sick funds in the research data base, the GFL database contains approximately 5-6% of the total sick fund population. Furthermore, sick fund participation is mandatory by German law for those with incomes below a predetermined level. Thus, the GFL database may not be fully representative of the whole German population.

10.10 **Other aspects**

10.10.1 *Study Funding*

Biogen Idec is the Sponsor of the study and is funding the study. All financial details are provided in the separate (sub-)contracts between the CROs and Biogen Idec.

11 **Protection of human subjects**

The data in the GFL research database are pseudonymized and the key for potential deidentification is kept by an independent third party trustee. No separate approval needs to be obtained since the process of the data collection and pseudonymization has already been approved in Germany in accordance with national law. GFL is authorized to perform the analyses on the pseudonymized data set without additional specific ethical approvals.

12 **Management and reporting of adverse events/adverse reactions**

According to the EMA good pharmacovigilance practice Module VI, safety reporting is not required for studies using secondary data sources, such as claims data. ((14), p22) If reports of adverse events/reactions are captured during the study they will be summarized as part of the final report.

13 **Plans for disseminating and communicating study results**

A final study report will be sent to Health Authorities within 12 months of data availability.

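### The only sensitivity analysis named for the off-label share covers missing codes; false MS codes under the one-claim rule are not examined

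*Protocol*

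**What the plan says.** - **Protocol 10.3.3:** on-label means aged 18 or over and diagnosed with MS. The identifying algorithms are to include "the presence of at least one medical claim with an ICD-10 code of MS for the indicated conditions" (G35.x). The section states no second claim, care setting or confirming MS drug. Users under 18 are off-label whatever their code.
- **Protocol 10.7.3:** the off-label proportion is 1 minus (patients using DMF on-label / all DMF patients). The one sensitivity analysis named reads: "Sensitivity analyses will be performed with regard to patients for whom the diagnostic code is missing".
- **Protocol 10.9.1:** "Presence of a diagnosis code on a medical claim is not positive presence of disease, as the diagnosis code may have been incorrectly applied".
- **Protocol 10.1:** the detail in the claims data, including diagnostic codes, "allows the efficient and valid identification of" off-label use.
- **Protocol 10.3 and 10.7.1:** the variables are preliminary. Refinements of their definitions and the complete list of analyses are left to the SAP, which is not at hand.

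**The concern.** A diagnosis rule based on codes can fail in two ways. An MS patient without a G35 code is counted as off-label. An adult without MS who carries a G35 code is counted as on-label. The sensitivity analysis named in 10.7.3 bears on the first failure only. The second arises when a single claim is accepted as evidence of MS, and 10.9.1 acknowledges that such a claim may be wrong.

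The second failure acts directly on the primary outcome. Each adult with a false G35 code moves from the off-label to the on-label count, so the reported off-label share falls by that one patient. Off-label use, psoriasis in particular, is what section 8 says the study is meant to find. A larger sample does not help, because the relative loss does not depend on the number of patients.

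**Working it through.** The study is descriptive and has no power calculation, so there is no planned figure to reproduce. The check has two parts: what the planned analyses vary, and how far each error could move the result.

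**Step 1. What the planned analyses vary.**
- 10.7.3: cases with a missing diagnosis are varied; the MS definition is not.
- 10.7.5: stratification by age and by indication, for secondary endpoints only; the MS definition is not varied.
- 10.7.4: tables by on-label and off-label status, with the classification taken as given.

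None of these recomputes the off-label share under a stricter MS definition.

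**Step 2. Model.** Observed off-label share = t(1 − f) + (1 − t)m, where
- t = true off-label share;
- f = probability that a truly off-label adult carries at least one G35 code;
- m = probability that an adult with MS has no G35 code.

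None of the three is in the documents, so all values are assumptions. All users are treated as adults, since the code does not affect the off-label status of those under 18.

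**Step 3. False MS codes only (m = 0).** Observed share = t(1 − f).

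| True share t | f = 10% | f = 25% | f = 50% |
|---|---|---|---|
| 2% | 1.8% | 1.5% | 1.0% |
| 5% | 4.5% | 3.75% | 2.5% |
| 10% | 9.0% | 7.5% | 5.0% |

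Section 10.5 projects about 500 MS initiators. With 500 as an illustrative denominator, a true 5% is 25 patients. At f = 50% about 12 would be seen, exact 95% interval 1.2% to 4.2%, which excludes 5%. At f = 10% (23 seen, 2.9% to 6.8%) and f = 25% (19 seen, 2.3% to 5.9%) the interval still includes 5%.

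**Step 4. Missed MS codes only (f = 0).** At t = 5% and m = 2%: 0.05 + 0.95 × 0.02 = 6.9%.

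**Step 5. Both errors.** They cancel when t × f = (1 − t) × m. At t = 5%:
- f = 10%: m = 0.005 / 0.95 = 0.53%;
- f = 50%: m = 0.025 / 0.95 = 2.6%.

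A small miss rate among the many MS patients can therefore offset a large false-code rate among the few others. At f = 50% and m = 2%: 0.025 + 0.019 = 4.4%.

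**Step 6. What a stricter rule would do.** Take 500 users, 25 truly off-label, no false codes at all, and suppose 5% of the 475 true MS users fail the strict rule. Then (25 + 0.05 × 475) / 500 = 48.75 / 500 = 9.75%. The strict result can rise well above the truth without a single false code to correct.

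**The case against.** The strongest reply is that this is SAP territory. The 10.3.3 wording says the algorithms will include the one-claim criterion, the definition is introduced as the primary one, and 10.3 leaves refinements to the SAP. That stands in part: one claim is a stated minimum, and the absence of a stricter analysis is established for the protocol only. A reader might infer that the sponsor has fixed one claim as sufficient and excluded any further test; the text does not go that far. The point survives because the protocol itself names a sensitivity analysis for its primary outcome and directs it at one error only.

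Second, the 10.7.4 tables by label status show prescriber specialty, comorbidities and the last MS drug, so many dermatology prescribers or psoriasis codes among on-label users might be noticed. That is a real but weak check. In the example with t = 5% and f = 50%, misclassified patients make up 12.5 of 487.5 on-label users (2.6%). At f = 10% they make up 2.5 of 477.5 (0.5%). The tables do not separate them out or recompute the proportion.

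Third, a reader might infer that off-label use will be understated overall. Steps 4 and 5 show why that does not follow.

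Fourth, a reader might see a contradiction between the validity wording in 10.1 and the limitation in 10.9.1. A design rationale and a disclosed source of error can stand together, so 10.1 need not change.

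**Conclusion.** The concern holds as a gap in one direction. For adults, the protocol states a one-claim MS criterion, admits that codes may be wrong, and names a sensitivity analysis that addresses possible false off-label classification but not false on-label classification.

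The size is unknown. Under assumed values of f from 10% to 50%, with no missed MS codes, a true 5% would be observed as 4.5% to 2.5%. With a 2% miss rate and no false codes it would be observed as 6.9%. The documents support neither set of values, so no net bias in either direction can be claimed. What can be said is that the protocol, as written, would not show how far the primary result depends on patients with a single G35 claim. The change is worthwhile and inexpensive; the primary definition does not need replacing.

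**What to change.** Keep the one-claim rule as the primary definition and add to 10.7.3:

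1. **One sensitivity analysis with a stricter MS definition for adults.** For example, G35 on at least two claims on different dates, or one inpatient G35 diagnosis, or one G35 claim plus a fill of a disease-modifying drug listed in 10.3.5. The exact rule can be set in the SAP before the data are analysed.
2. **Both off-label proportions side by side, as a range.** The strict figure cannot be lower than the primary one, because it only removes patients from the on-label group. It should be read as the upper bound of the range and not as a corrected estimate, since it also reclassifies some true MS patients, such as the newly diagnosed.
3. **A short description of adults who meet only the one-claim rule,** by prescriber specialty and presence of a psoriasis code. This helps to tell probable false codes from MS patients with few claims, which the gap between the two proportions cannot do.

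The cost is one further run of the classification and one small table. Section 10.4 lists inpatient and outpatient diagnosis codes, prescriber specialty and dated dispensing records with ATC codes among the database variables, so no new data are needed.

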10.5 Study Size

In a preliminary feasibility analysis, approximately 8,000 MS patients were identified in the GFL research database between 2007 and 2011. Based on market uptake projections, approximately 500 MS patients in the GFL research database would be expected to initiate treatment with DMF within 18 months of product launch in Germany. Due to the voluntary participation of German sick funds in the research database, it cannot be guaranteed that this sample size remains constant in the future. The final sample size of this study will depend on the actual market uptake of DMF and future sick fund participation.

This study is strictly descriptive (i.e. no hypothesis testing will be conducted); therefore no power calculations have been conducted.

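### The on-label rule takes any adult MS code, although the protocol names relapsing-remitting MS as the indication, so off-label use by MS type cannot be seen

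*Protocol*

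**What the plan says.** Section 8 of the protocol closes its summary of the Phase 3 evidence with: "DMF also demonstrated a positive benefit-risk balance for the proposed indication of RRMS". This is the only place where the protocol ties the indication to a type of MS. The synopsis and Section 10.1 give the standard of comparison when they say that the observation period should reveal "any off-label use (per product information").

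Section 10.3.3 then sets the on-label group: "DMF 'on-label' prescriptions will be primarily defined as prescriptions for patients who are ≥ 18 years of age and diagnosed with MS". The algorithm requires "at least one medical claim with an ICD-10 code of MS for the indicated conditions (G35.x for MS"), with no restriction on MS type. Off-label use is "prescriptions for patients without an MS diagnosis or for patients who are < 18 years of age and diagnosed with MS". The synopsis names the same two kinds of off-label use: "any DMF prescription for MS patients <18 years of age, or for patients diagnosed with non-MS indications, such as psoriasis".

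Tables 1 and 2 divide patients by age 18 and by MS, psoriasis or other diagnosis. Section 10.7.3 computes the off-label proportion as one minus on-label patients over all DMF patients. The one sensitivity analysis planned there concerns missing diagnostic codes.

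**The concern.** The stated standard and the operational rule do not match. If the label is what Section 8 names, an adult treated for a non-relapsing type of MS is outside it. The rule still puts that patient in the on-label numerator, no cell of Table 2 would show the case, and no planned analysis would bring it out.

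This touches the primary result. The objective reads: "The primary objective of this study is to estimate the proportion of DMF use that is prescribed “on-label” versus “off-label” in Germany". The user group that the protocol sizes is the MS group, so the unseen category lies inside the largest expected part of the sample. A reader of the final report could take the on-label share as agreement with the indication, when it shows only that the patient was an adult with an MS code. Section 10.1 encourages that reading, because it presents the diagnostic codes as a valid means of finding off-label use.

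**Working it through.** **Inputs from the protocol**
- Expected MS users, Section 10.5: "approximately 500 MS patients in the GFL research database would be expected to initiate treatment with DMF within 18 months". Write M = 500.
- Primary formula, Section 10.7.3: off-label = 1 − on-label / N, where N is all DMF patients.

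**Inputs that the protocol does not give (assumed)**
- O, users without an MS claim: 0 to 50, so N = 500 + O.
- s, the non-RRMS share of adult MS users: 0 to 20%.
- All 500 MS users are adults with a G35 claim.

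**The plan's own figure.** The 500 cannot be reproduced, because the market projection behind it is not shown. Against the roughly 8,000 MS patients in Section 10.5 it implies an uptake of 500 / 8,000 = 6.25%. The argument below does not depend on its exact value.

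**Step 1: off-label proportion under each rule**
- Protocol rule (any G35.x): p0 = 1 − M/N = O/N.
- RRMS-only rule: p1 = 1 − M(1 − s)/N.
- Difference: p1 − p0 = s × M/N. It is never negative, and with MS users present it is zero only if s = 0.

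**Step 2: numbers**

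| Users without MS (O) | N | Protocol rule | s = 2% | s = 5% | s = 10% | s = 20% |
|---|---|---|---|---|---|---|
| 0 | 500 | 0.00% | 2.00% | 5.00% | 10.00% | 20.00% |
| 10 | 510 | 1.96% | 3.92% | 6.86% | 11.76% | 21.57% |
| 25 | 525 | 4.76% | 6.67% | 9.52% | 14.29% | 23.81% |
| 50 | 550 | 9.09% | 10.91% | 13.64% | 18.18% | 27.27% |

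Example: O = 25 and s = 5% give p0 = 25/525 = 4.76% and p1 = 1 − 475/525 = 9.52%.

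**Step 3: which summary is stable.** For each 1% of s (5 patients in 500) the shift is 5/500 = 1.00 point at O = 0 and 5/550 = 0.91 point at O = 50. The ratio p1/p0 is not stable. For s from 2% to 10% it runs from 2.0 to 6.0 at O = 10, from 1.4 to 3.0 at O = 25, and from 1.2 to 2.0 at O = 50. Only the absolute shift should be quoted.

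**Step 4: the error in the other direction.** Let u of the O users be adults with RRMS who have no G35 claim in the data searched. They are counted as off-label. By an RRMS indication the off-label proportion would be (O − u + sM)/N, against a reported O/N. The net error, reported minus true, is (u − sM)/N. At s = 5%, sM = 25, so 25 uncoded RRMS patients would cancel the effect exactly. Neither u nor s is given, so the sign of the net error cannot be settled from the protocol.

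**The case against.** The strongest reply is that the label is not in the document. Section 8 speaks of a proposed indication in a background sentence, and the same section says that the drug was developed for MS. That stands: the protocol alone does not prove that adult non-relapsing MS is off-label. But the protocol states no broader indication that would justify accepting every MS code, so the sections still have to be reconciled.

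Second, Section 10.3 calls the variables preliminary and leaves refinements to the SAP, and Section 10.3.3 says only how use is primarily defined. This carries less weight. The split is fixed in the synopsis, in Section 10.3.3 and in two tables, and nothing announces an analysis by MS type.

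Third, the study is aimed mainly at use outside MS, especially in children with psoriasis, and Tables 1 and 2 serve that aim. That is fair, but the primary objective is worded as on-label against off-label without that limit.

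Fourth, the claims may not carry MS type. No section says whether G35 subcodes are available or well filled. The three-digit depth in Section 10.3.2 applies to comorbidities, and Section 10.9.1 warns in general of wrong codes and missing clinical detail. This stands as a limit on the fix. Section 10.9.1 does not mention MS type, so it does not disclose the gap.

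A reader might also infer that the plan is blind to all off-label use within MS. It is not: MS patients under 18 are classed as off-label and have their own cell in Table 2.

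**Conclusion.** The point holds in a limited form. The on-label definition does not match the only indication that the protocol names, and the primary analysis cannot show use in adults with non-relapsing MS as off-label. Taken alone, this rule can only lower the off-label proportion, by s × M/N. That is about 0.9 to 1.0 percentage point per 1% non-RRMS share, for about 500 MS users and an assumed 0 to 50 others. It rests on the label being limited to RRMS, as Section 8 suggests but does not establish, and on s being above zero, which the plan as written could not reveal.

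Two stronger conclusions are tempting and are not supported. One is that the reported off-label proportion will be too low overall, or is a lower bound. RRMS patients without a G35 claim push it up, and the sensitivity analysis on missing codes covers that only in part. The other is that the true figure is some multiple of the reported one. Any such multiple comes from the number of non-MS users that one chooses to assume.

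**What to change.** 1. Quote the indication from the product information in the protocol, and reconcile Sections 8 and 10.1 with the definitions in the synopsis and Section 10.3.3.
2. If that indication is limited to RRMS and the G35 subcode is available, split the adult MS cell of Tables 1 and 2 into relapsing-remitting, non-relapsing and unspecified. Report the off-label proportion twice, with unspecified patients counted first as on-label and then as off-label.
3. If the subtype is not available, label the category *adult MS use (any type)*. State that off-label use by MS subtype is not measured and that this omission alone lowers the off-label proportion. Do not call the result a lower bound.
4. In that case also qualify the statement in Section 10.1 that the codes validly identify off-label use, and add MS type to the limitations in Section 10.9.1.

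The cost is protocol and SAP wording and, where subcodes exist, one table split. Availability of the subcode should be confirmed with the database holder before data retrieval, planned for Q4 2016. The downside is that some codes will be unspecified, so the primary figure becomes a range.
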